### 10.4.5 Other Efficacy Analyses

All the efficacy endpoints will be analyzed by the reasons of apremilast failure at screening: 1) failure to achieve adequate response, 2) loss of adequate response or 3) intolerability.

### 10.5 Safety Analyses

# 10.5.1 Adverse Events

Safety analyses will be conducted using the full analysis set. The Medical Dictionary for Regulatory Activities (MedDRA) version 18.1 or later will be used to code all adverse events (AEs) to a system organ class and a preferred term. Subject incidence of adverse events will be summarized for all treatment-emergent, serious, treatment-related, serious treatment-related, those leading to withdrawal of investigational product, those leading to study withdrawal, and fatal.

The subject incidence of all treatment-emergent, serious, treatment-related, serious treatment-related, those leading to withdrawal of investigational product, those leading to study withdrawal, fatal, and fatal treatment-related adverse events will be tabulated by system organ class and preferred term in descending order of frequency.

A summary of all treatment-emergent adverse events occurring in at least 5% of the subjects will be provided by preferred term in descending order of frequency.

Subgroup analyses by age group (< 65,  $\geq 65$ ), sex (male, female), race (White, non-white) may be presented for AEs summarized by system organ class and preferred term in descending order of frequency.

Subject listings of all treatment-emergent, serious, treatment-related, those leading to withdrawal of investigational product, those leading to study withdrawal, and fatal adverse events will be provided.

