1.3 Safety

To evaluate the safety and tolerability of etanercept in apremilast failures.

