9.2.2 Adverse Events

9.2.2.1 Reporting Procedures for Adverse Events That do not Meet Serious Criteria

The investigator is responsible for ensuring that all adverse events observed by the investigator or reported by the subject that occur after first dose of investigational product through the end of treatment period are reported using the Event CRF.

The investigator must assign the following adverse event attributes:

- Adverse event diagnosis or syndrome(s), if known (if not known, signs or symptoms),
- Dates of onset and resolution (if resolved),
- Severity [and/or toxicity per protocol],
- Assessment of relatedness to etanercept, and
- Action taken

The adverse event grading scale used will be the Common Terminology Criteria for Adverse Events (CTCAE) version 4.0. The grading scale used in this study is described in Appendix A. The investigator must assess whether the adverse event is possibly related to the investigational product. This relationship is indicated by a "yes" or "no" response to the question: Is there a reasonable possibility that the event may have been caused by the investigational product?

If the severity of an adverse event changes from the date of onset to the date of resolution, record as a single event with the worst severity on the Adverse Event Summary CRF.

The investigator is responsible for reviewing laboratory test results and determining whether an abnormal value in an individual study subject represents a clinically significant change from the subject's baseline values. In general, abnormal laboratory findings without clinical significance (based on the investigator's judgment) are not to be recorded as adverse events. However, laboratory value changes that require treatment or adjustment in current therapy are considered adverse events. Where applicable, clinical sequelae (not the laboratory abnormality) are to be recorded as the adverse event.

The Investigator is expected to follow reported adverse events until stabilization or reversibility.

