### 10.5.6 Other Safety

The analyses of subject incidence of all treatment-emergent, serious, treatment-related, serious treatment-related, those leading to withdrawal of investigational product, those leading to study withdrawal, fatal, and fatal treatment-related adverse events tabulating by system organ class and preferred term in descending order of frequency will be repeated by the reasons of apremilast failure at screening: 1) failure to achieve adequate response, 2) loss of adequate response or 3) intolerability.

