# Appendix B. Code Fragments

Appendix C. Patient-reported Outcome Forms/Instruments

### Appendix D. Reference Values/Toxicity Grades

Adverse event severity is graded based on the National Cancer Institute Common Toxicity Criteria for Adverse Events (CTCAE) version 4.0 (see Protocol Appendix B).

Laboratory toxicity is graded based on the National Cancer Institute Common Toxicity Criteria (CTC) version 4.0 with the following additions:

	Grade				
	0	1	2	3	4
BUN	WNL	>1.5 – 2.0 x ULN	>2.0 – 3.0 x ULN	>3.0 – 4.0 x ULN	>4.0 x ULN
HGB	WNL	>ULN	>(ULN+1) – (ULN+2)	>(ULN+2)	-
Urine Protein	NEG, NEGATIVE, TRACE, NORMAL, NOT DETECTED	+, +1, 1+	++, +2, 2+, +++, +3, 3+	++++, +4, 4+	-
Platelet Count	WNL	> ULN - 1.0x10  /L	> 1.0x10  /L	-	-
Leukocyte Count	WNL	> ULN 2.0x10  /L	> 2.0x10  /L - 4.0x10  /L	> 4.0x10  /L	-

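### Adverse events are graded by CTCAE, but no planned summary of clinical adverse events uses the grade, so tolerability is only partly reported

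*SAP*

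**What the plan says.** The safety objective in Protocol 1.3 is "To evaluate the safety and tolerability of etanercept in apremilast failures".

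Protocol 9.2.2.1 makes severity one of the attributes the investigator must assign, and names the scale: "The adverse event grading scale used will be the Common Terminology Criteria for Adverse Events (CTCAE) version 4.0". If severity changes over the course of an event, the site is to "record as a single event with the worst severity on the Adverse Event Summary CRF". SAP Appendix D restates the point: "Adverse event severity is graded based on the National Cancer Institute Common Toxicity Criteria for Adverse Events (CTCAE) version 4.0".

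The outputs are in SAP 10.5.1. The overall summary reads "Subject incidence of adverse events will be summarized for all treatment-emergent, serious, treatment-related, serious treatment-related, those leading to withdrawal of investigational product", and adds events leading to study withdrawal and fatal events. The detailed tables cover the same classes plus one more, ending with "fatal, and fatal treatment-related adverse events will be tabulated by system organ class and preferred term in descending order of frequency". SAP 10.5.6 takes those detailed tables and says that the analyses "tabulating by system organ class and preferred term in descending order of frequency will be repeated by the reasons of apremilast failure at screening".

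Protocol 10.3.3 plans tables of all treatment-emergent, fatal and serious events, events leading to withdrawal from product, and treatment-emergent events described only as significant. Both documents use CTC grades for laboratory parameters (Protocol 10.3.3; SAP 10.5.2).

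**The concern.** Seriousness and severity are different attributes. Protocol 9.1.3 defines seriousness by outcome or consequence: death, threat to life, hospitalisation, disability, congenital anomaly or other medical importance. Severity is how intense the event was. An event can be severe and meet none of the serious criteria, and for a tolerability objective such events are of direct interest.

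This is an open-label, single-arm study, so its safety evidence is descriptive. The trial also sets out to enrol 10 to 20 subjects who could not tolerate apremilast, and SAP 10.5.6 repeats the adverse-event tables for them. Whether their events on etanercept were mild or severe is a natural question for that group. If the planned tables are produced exactly as written, the report will contain no incidence of severe clinical adverse events, although the grade is in the database.

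**Working it through.** The plan states no figure on this point, so there is nothing to reproduce. The check is to go through every safety output that involves events or grades and ask whether it uses the adverse-event grade.

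| Output | Source | Split by | Adverse-event grade used? |
|---|---|---|---|
| Overall summary | SAP 10.5.1 | 7 classes: treatment-emergent, serious, related, serious related, product withdrawal, study withdrawal, fatal | No |
| Organ class and preferred term tables | SAP 10.5.1 | The same 7 plus fatal related = 8 classes | No |
| Events in at least 5% of subjects | SAP 10.5.1 | Preferred term | No |
| Optional repeats by age, sex, race | SAP 10.5.1 | Organ class and preferred term | No |
| Repeats by reason for apremilast failure | SAP 10.5.6 | The same 8 classes, 3 reasons | No |
| Protocol event tables | Protocol 10.3.3 | Treatment-emergent, fatal, serious, product withdrawal, *significant* | None stated; *significant* is undefined |
| Disease related events | Protocol 10.3.3 | All, fatal | No |
| Subject listings | SAP 10.5.1 | 6 classes | Columns not specified |
| Laboratory toxicity | Protocol 10.3.3; SAP 10.5.2 | CTC grade | Grades are of laboratory values, not clinical events |

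Of the 8 tabulated classes, the fatal and fatal related tables would gain nothing from a severity split. That leaves 8 − 2 = 6 classes where a grade would add information.

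Intensity appears once more, in the SAP Section 6 definition of a treatment-emergent event. There it decides whether a worsening pre-existing event counts at all. It is not a way of reporting the events that do count.

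The significant-events table was then traced. It is in Protocol 10.3.3. It is not in SAP 10.5.1. SAP Section 11 lists one change from the protocol, the repeat of analyses by reason for apremilast failure, and does not mention this table.

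An illustration shows what the planned tables cannot separate. The counts are assumptions, because the documents give no rate. Take two possible outcomes with N = 80 and the same number of subjects with any treatment-emergent event, the same preferred terms, and the same serious, related and withdrawal counts. In one, 2 subjects had a non-serious Grade 3 event that did not lead to withdrawal; in the other, 12 did. Every planned summary of clinical adverse events would be identical.

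A Grade 3 or higher row would separate them. The exact 95% limits are the 0.025 quantile of Beta(x, 80 − x + 1) and the 0.975 quantile of Beta(x + 1, 80 − x), with the lower limit 0 when x = 0:

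- 0/80 = 0%: 0 to 4.5% (upper limit 1 − 0.025^(1/80) = 0.045)
- 2/80 = 2.5%: 0.3 to 8.7%
- 4/80 = 5%: 1.4 to 12.3%
- 8/80 = 10%: 4.4 to 18.8%
- 12/80 = 15%: 8.0 to 24.7%

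So a severity row would be informative at this sample size, including when no severe event occurs. In the intolerability group it would be much less precise: with 0 of 20 the upper limit is 1 − 0.025^(1/20) = 16.8%.

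**The case against.** The strongest reply is that tolerability is covered in other ways and that no commitment is broken. Much of this stands.

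- A reader might infer that no safety table uses a CTC grade. That is not so. Laboratory assessments are one of the two listed safety endpoints, and they get shift tables, summaries by grade, and Grade 3 and 4 incidence. The gap concerns clinical adverse events only.
- A reader might infer that the tolerability objective goes unanswered, or that the adverse-event tables are the only evidence for it. The documents do not support this. Events leading to withdrawal from product and from study are summarised, tabulated and listed. SAP 10.5.4 reports missed doses, and disease related events are tabulated under Protocol 10.3.3.
- A reader might infer that every severe non-serious event is lost among the mild ones. Those that lead to withdrawal are separated. Protocol 9.1.3 also allows an investigator to classify a clinically important event as serious under the medically important criterion, so some would move to the serious tables. That step is discretionary and does not cover all of them.
- The attribute list and the worst-severity rule sit under the heading for non-serious events, and Protocol 9.2.2.2 repeats neither for serious events. Those two provisions should not be cited as an explicit rule for serious events. The sentence naming the scale, and SAP Appendix D, are worded for adverse events generally, and the events at issue here are the non-serious ones.
- Listings of all treatment-emergent events for about 80 subjects may show grade. The SAP neither promises nor excludes it. A listing would allow counting by hand but gives no planned incidence.
- The significant-events table might have carried severity. Because the word is undefined, it cannot be counted as a severity table, nor can its absence from the SAP be read as a decision to drop one.

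It is also true that neither document promises an adverse-event table by grade. This is a gap in what is reported, not a departure from a stated plan.

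**Conclusion.** The point holds in this form: adverse events are graded, and no planned summary of clinical adverse events uses the grade. The consequence is confined to severe events that are not serious and do not lead to withdrawal, which are counted like mild ones. The tolerability objective is therefore answered in part.

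The gap runs through the overall summary and the 6 detailed event classes where grade would be informative, and through their repeats by the 3 reasons for apremilast failure. The number of subjects concerned cannot be estimated from the documents. The primary endpoint and all efficacy results are unaffected.

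Separately, the significant-events table is an unrecorded mismatch between protocol and SAP. That is established by the text alone and does not depend on what *significant* was meant to cover.

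The conclusion assumes that the SAP lists its safety outputs completely, and that the grade is captured on the Event CRF as Protocol 9.2.2.1 implies.

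**What to change.** 1. In SAP 10.5.1, add subject incidence of treatment-emergent adverse events by worst CTCAE grade, by system organ class and preferred term, counting each subject once at the highest grade.
2. Add a Grade 3 or higher row to the overall summary and to the treatment-related summary.
3. Either define the significant treatment-emergent adverse-event table of Protocol 10.3.3 and carry it into SAP 10.5.1, or record its removal in SAP Section 11.

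When making these edits, confirm that the grade is entered for serious events as well as non-serious ones, so that the Grade 3 or higher row is complete. The cross-reference in SAP Appendix D also needs correcting: it sends the reader to Protocol Appendix B for the CTCAE scale, which is in Protocol Appendix A.

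The cost is a few sentences in the SAP and one or two tables. The grade is already collected, so no visit, form or clinical rule changes. Writing this in before the data are reviewed also avoids choosing afterwards how to present severity.

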# 10.5.2 Laboratory Test Results

Laboratory parameters will be summarized descriptively by study visit for all subjects in the full analysis set. Laboratory analytes are provided in the protocol Table 2. In addition, laboratory toxicities based on the Common Toxicity Criteria (CTC) grading

system will be summarized descriptively by study visit. Modifications to CTC version 4.0 used for this analysis are described in Appendix D. Subject incidence of analytes with CTC Grades 3 and 4 will be provided.

### 10.5.3 Vital Signs

Vital signs will be summarized descriptively at baseline for all subjects in the full analysis set.

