10.3.3 Safety Endpoints

Safety endpoints will be summarized descriptively based on the full analysis set. Subject incidence of all treatment-emergent adverse events will be tabulated by system organ class and preferred term. Tables of fatal adverse events, serious adverse events, adverse events leading to withdrawal from investigational product, and significant treatment-emergent adverse events will be provided.

Subject incidence of disease related events and fatal disease related events will be tabulated by system organ class and preferred term.

Laboratory parameters and vital signs will be summarized by study visit. Shift tables of the worst on-study laboratory toxicity based on CTCAE version 4.0 relative to baseline will be tabulated. Subject listings of grades 3 and 4 laboratory toxicities will be provided.

11. **REGULATORY OBLIGATIONS**

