### Appendix A. Technical Detail and Supplemental Information Regarding Statistical Procedures and Programs

### Visit Windows for All Efficacy and Selected Safety Evaluations

Per protocol, visits are to be performed within 5 days of the protocol-specified study day. To allow for variations in scheduling, the following visit windows will be applied to all efficacy and select safety evaluations (ie, vital signs, laboratory evaluations, and physical measurements) to assign a most appropriate nominal visit for analysis. If more than one actual visit falls within the same defined window, the closest visit to the target day (ie, scheduled visit week x 7 + 1) will be considered for analysis. If two assessment dates are the same distance from the target day, then the latest visit will be considered for analysis. Any visit that falls in an unscheduled visit for that assessment (eg, a DLQI assessment done at week 16) will be excluded from the analysis and reported in listings only.

Visit	Target	Window	Interval
Week	Day	Definition	(days)
Baseline	1	Last Evaluation prior to or on Study Day 1	n/a
Week 4	29	Study Day 15 to 42	28
Week 8	57	Study Day 43 to 70	28
Week 12	85	Study Day 71 to 98	28
Week 16	113	Study Day 99 to 126	28
Week 20	141	Study Day 127 to 154	28
Week 24	169	Study Day 155 to 182	28

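### The SAP summarises vital signs at baseline where the protocol promises every visit, does not declare the change, and leaves several other protocol safety outputs unnamed

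*SAP*

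**What the plan says.** **Vital signs.** Protocol 10.3.3 treats laboratory values and vital signs together: "Laboratory parameters and vital signs will be summarized by study visit". The SAP separates them. SAP 10.5.2 keeps the by-visit summary for laboratory parameters, but SAP 10.5.3 reads "Vital signs will be summarized descriptively at baseline for all subjects in the full analysis set". SAP Appendix A lists vital signs among the variables to be windowed: "the following visit windows will be applied to all efficacy and select safety evaluations (ie, vital signs, laboratory evaluations, and physical measurements".

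**Other outputs in protocol 10.3.3.**
- Disease related events: "Subject incidence of disease related events and fatal disease related events will be tabulated by system organ class and preferred term".
- Laboratory shifts: "Shift tables of the worst on-study laboratory toxicity based on CTCAE version 4.0 relative to baseline will be tabulated".
- Laboratory listings: "Subject listings of grades 3 and 4 laboratory toxicities will be provided".
- The last item in the list of adverse event tables: "and significant treatment-emergent adverse events will be provided".

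None of these is named in SAP 10.5.1 to 10.5.6. The nearest laboratory outputs in SAP 10.5.2 are a by-visit summary of toxicity grades and an incidence: "Subject incidence of analytes with CTC Grades 3 and 4 will be provided". Disease related events appear in the SAP only as a definition, with a time window, in SAP 6.

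**Declared changes.** SAP 11 declares one change, which is an addition: repeating the analyses by reason for apremilast failure.

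**The concern.** Safety and tolerability is a stated objective in both documents. The SAP is what the programmers follow. Where it narrows a protocol output without saying so, the output may simply not be produced. For vital signs, a baseline summary describes the population at entry and says nothing about change on etanercept.

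For the unnamed outputs, a reader of the SAP cannot tell whether they were dropped or only not restated. Two of them carry information that the named SAP tables do not replace. The shift table shows each subject's worst laboratory grade against where that subject began. The disease related event table is the only planned tabulation of ordinary psoriasis worsening recorded as an event.

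**Working it through.** No sample size, power or alpha figure is involved. The check is an output-by-output comparison of protocol 10.3.3 with SAP 10.5, followed by a look at whether the nearest SAP output could serve instead.

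**Step 1. Match the outputs.**

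| Protocol 10.3.3 output | Nearest place in the SAP | Status |
|---|---|---|
| 1. Treatment-emergent AEs by MedDRA class and term | 10.5.1 | carried |
| 2. Fatal AEs | 10.5.1 | carried |
| 3. Serious AEs | 10.5.1 | carried |
| 4. AEs leading to withdrawal of product | 10.5.1 | carried |
| 5. Laboratory parameters by visit | 10.5.2 | carried |
| 6. Vital signs by visit | 10.5.3, at baseline | changed |
| 7. Significant treatment-emergent AEs | none (10.5.1 has a table with a 5% frequency cut-off) | not named |
| 8. Disease related events | definition in SAP 6 only | not named |
| 9. Fatal disease related events | none | not named |
| 10. Shift of worst laboratory grade against baseline | by-visit grade summary in 10.5.2 | not named |
| 11. Grade 3/4 laboratory listings | Grade 3/4 incidence in 10.5.2 | not named |

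Carried 5 + changed 1 + not named 5 = 11. Rows 8 and 9 come from one protocol sentence; counted together, the unnamed outputs number four. SAP 11 declares none of the six differences.

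**Step 2. Vital signs.** Protocol Table 1 schedules vital signs, from Day 1 on, at Day 1 and Weeks 4, 8, 12, 16, 20 and 24/ET: 7 visits. A baseline summary covers 1, so 7 − 1 = 6 have none. With about 80 subjects and no dropout or missed visits, that is up to 80 × 6 = 480 planned assessments.

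SAP 10.5.3 does not say that baseline is the only time point, but no other SAP section adds a later vital-sign summary. The general sentence on safety endpoints in SAP 10.1 does not fill the gap, because SAP 4.1.3 lists those endpoints as adverse events and laboratory assessments.

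**Step 3. Can the by-visit laboratory summary stand in for the shift table?** After Day 1, protocol Table 1 schedules hematology and chemistry only at Week 12 and Week 24/ET. SAP Appendix A gives these the windows Days 71 to 98 and Days 155 to 182. An assessment that falls at a visit not scheduled for it is listed but not analysed. An early-termination draw near Week 16, for example, would not enter the by-visit summary. If such a draw held the subject's worst grade, the by-visit table would miss it. The documents give no basis for saying how many results this affects.

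**Step 4. Can the AE tables stand in for the disease related event table?** Under protocol 9.1.1 and SAP 6, ordinary worsening of psoriasis is not an adverse event. It becomes reportable as one if it is more severe than expected or, under protocol 9.1.1, if the investigator suspects the product. Protocol 9.2.2.1 collects non-serious AEs only to the end of the treatment period. Protocol 9.2.1 and 9.2.2.2 collect disease related events and serious AEs through the 30-day follow-up, and Table 1 agrees: the AE row has no mark at the 30-day call. So ordinary worsening is absent from the AE tables throughout, and after treatment ends only serious worsening must be reported as an adverse event.

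**The case against.** The strongest counter-argument is that, vital signs apart, the SAP is silent and does not conflict with the protocol. SAP 1 says the document gives detail on analyses the protocol outlines, and SAP 6 keeps a disease related event definition with its own window. SAP 11 lists changes, and failing to restate an output is not shown to be a change. This stands: a reader might infer that the sponsor dropped the unnamed outputs, but the documents show only that they are neither named nor declared dropped.

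A reader might also infer that the SAP contradicts itself, because Appendix A windows vital signs at Weeks 4 to 24. It does not go that far. Appendix A assigns nominal visits and promises no summary; it also names physical measurements, for which SAP 10.5 plans no by-visit summary either. The windows are unused, and the contradiction is between SAP 10.5.3 and protocol 10.3.3.

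It is tempting to size the laboratory gap by the calendar days outside the Week 12 and Week 24 windows, or the disease related event gap by the days between the Week 24 visit and the end of follow-up. Neither count measures lost results or events. On-time scheduled draws fall inside their windows, so only early-termination or unscheduled draws are exposed. The Grade 3/4 incidence in SAP 10.5.2 is not stated to be by visit and may pick up some of these, and Appendix A does foresee listings of them.

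Finally, vital signs are not a listed safety endpoint in either document, and protocol 7.3.6 sends abnormalities judged to be adverse events to the Event CRF. This limits the consequence but does not remove the mismatch.

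**Conclusion.** The vital-sign point holds as a direct, undeclared difference between SAP 10.5.3 and protocol 10.3.3. Its size is six of seven visits from Day 1 without a summary if the SAP is followed literally. The remaining outputs (five counted singly, four if the two disease related event tables are taken together) need to be confirmed or declared. Of these, the shift table is the most useful to restore, because the by-visit grades do not replace it.

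Severity is minor. Only descriptive safety reporting is affected, the primary estimate is untouched, and the underlying data are collected. The conclusion rests on reading SAP 10.5.3 as the only vital-sign analysis and on no separate output list restoring the missing items; neither document refers to one. The number of laboratory results or disease related events that would go untabulated is unknown.

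**What to change.** - **SAP 10.5.3:** replace *at baseline* with *by study visit*, using the Appendix A windows.
- **SAP 10.5.2:** add shift tables of worst post-baseline CTCAE grade against baseline. Take the worst from all post-baseline results, including early-termination and unscheduled draws, and say that the listings-only rule in Appendix A does not apply to this table. Add the Grade 3/4 subject listings.
- **SAP 10.5.1:** add incidence of disease related events and of fatal ones, by MedDRA class and term, using the SAP 6 window.
- **Significant treatment-emergent AEs:** neither document defines *significant*, so the table cannot be programmed as it stands. Either define the term and add the table, or declare it dropped in SAP 11.
- **SAP 11:** declare and justify any other protocol 10.3.3 output that is deliberately omitted.

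The cost is SAP wording and a few extra standard tables and listings. No new data are needed.
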